### **5.3.5.10 Hospitalization or Prolonged Hospitalization**

Any AE that results in hospitalization or prolonged hospitalization should be documented and reported as a SAE (per the definition of SAE in Section 5.1.2), except as outlined below.

The following hospitalization scenarios are not considered to be *an* SAE:

- Hospitalization for respite care
- Planned in-clinic stay for HVs in SAD and MAD portions of Part 1.
- Planned in-clinic stay of patients in Part 2 (optional) for intensive PK sampling or because of flu-like symptoms/pyrexia (Part 2, Cohort 4) *as per Section 5.2.1*.

- Hospitalization for a pre-existing condition, provided that all of the following criteria are met:
  - The hospitalization was planned prior to the study or was scheduled during the study when elective surgery became necessary because of the expected normal progression of the disease
  - The HV/patient has not suffered an AE.
- *If for administrative reasons, e.g. the patient lives far way and is kept in the clinic/hospital for patient and/or site convenience (Part 2, Cohort 4).*

#### **5.3.5.11 Overdoses**

Study drug overdose is the accidental or intentional use of the drug in an amount higher than the dose being studied. An overdose or incorrect administration of study drug is not an AE unless it results in untoward medical effects.

Any study drug overdose or incorrect administration of study drug should be noted on the Study Drug Administration eCRF. All AEs associated with an overdose or incorrect administration of study drug should be recorded on the AE eCRF. If the associated AE fulfills serious criteria, the event should be reported to the Sponsor immediately (i.e., no more than 24 hours after learning of the event; see Section 5.3.8).

#### **5.3.6 Immediate Reporting Requirements from Investigator to Sponsor**

Certain events require immediate reporting to allow the Sponsor to take appropriate measures to address potential new risks in a clinical trial. The Investigator must report such events to the Sponsor immediately; under no circumstances should reporting take place more than 24 hours after the Investigator learns of the event. The following is a list of events that the investigator must report to the Sponsor within 24 hours after learning of the event, regardless of relationship to study drug:

- SAE
- Non-serious AE of special interest
- Pregnancies

The Investigator must report new significant follow-up information for these events to the Sponsor immediately (i.e., no more than 24 hours after becoming aware of the information). New significant information includes the following:

- New signs or symptoms or a change in the diagnosis
- Significant new diagnostic test results
- Change in causality based on new information
- Change in the event's outcome, including recovery
- Additional narrative information on the clinical course of the event

Investigators must also comply with local requirements for reporting SAEs to the local health authority and IEC/IRB.

### **5.3.7 Emergency Medical Contacts**

To ensure the safety of HVs/patients, access to the Medical monitors is available 24 hours a day 7 days a week. Medical monitors contact details are listed in the "Protocol Administrative and Contact Information & List of Investigators".

### **5.3.8 Reporting Requirements for Serious Adverse Events and Non-Serious Adverse Events of Special Interest**

#### **5.3.8.1 Events that Occur prior to Study Drug Initiation**

After informed consent has been obtained but prior to initiation of study drug, only serious adverse events caused by a protocol-mandated intervention should be reported. The Serious Adverse Event/Adverse Event of Special Interest Reporting Form provided to investigators should be completed and submitted to the SAE Responsible immediately (i.e., no more than 24 hours after learning of the event).

#### **5.3.8.2 Events that Occur after Study Drug Initiation**

For reports of serious adverse events and non-serious adverse events of special interest (see Sections 5.1.2 and 5.1.3) that occur after initiation of study drug, investigators should record all case details that can be gathered on the Serious Adverse Reporting Form and forward this form to the SAE Responsible within 24 hours.

In the case of electronic reporting, investigators should record all case details that can be gathered immediately (i.e., within 24 hours after learning of the event) on the appropriate Serious Adverse Event / Adverse Event of Special Interest eCRF form and submit the report via the electronic data capture (EDC) system. A report will be generated and sent to the Sponsor's Safety Risk Management department.

In the event that the EDC system is unavailable, the Serious Adverse Event/Adverse Event of Special Interest Reporting Form provided to investigators should be completed and submitted to the SAE Responsible immediately (i.e., no more than 24 hours after learning of the event).

Once the EDC system is available, all information will need to be entered and submitted via the EDC system.

### **5.3.9 Reporting Requirements for Pregnancies**

#### **5.3.9.1 Pregnancies in Female Healthy Volunteers/Patients**

A female subject/patient of childbearing potential will be instructed to immediately inform the Investigator if she becomes pregnant until the end of the follow-up period of 28 days in Part 1 or 6 weeks in Part 2.

A Clinical Trial Pregnancy Reporting Form should be completed by the Investigator and submitted to the Sponsor within 24 hours after learning of the pregnancy in Part 1 or Part 2. Pregnancy should not be recorded on the AE eCRF. The Investigator should discontinue study drug and counsel the HV/patient, discussing the risks of the pregnancy and the possible effects on the fetus. Monitoring of the patient should continue until conclusion of the pregnancy.

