  - b. The reliability of sexual abstinence should be evaluated in relation to the duration of the clinical trial and the preferred and usual lifestyle of the patient. Periodic abstinence and withdrawal are not acceptable methods of contraception.
15. Negative pregnancy test on Day -1 for female patients.

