## **Part 2: Chronic Hepatitis B Patients**

In Part 2, RO7020531 or matching placebo will be administered orally to patients every other day from Day 1 through to Day 41 (*unless in Cohort 4 in case of QW dosing as dose modification*). In total, up to 21 doses will be given. The dose level for the Cohort 1 in patients will be determined upon completion of Part 1 (see Section 3.1.2.2). The number of capsules per intake will reflect the dose level for a cohort and will be defined prior to dosing of the first patient in a cohort. For every study drug administration, the dose will be composed of the appropriate combination of 1 mg, 10 mg and 100 mg capsules.

*Cohorts 1, 2, and 3 will include 10 patients (8 active and 2 placebo). Every dose will be given in the fasted state (patients will not eat 2 hours before and 2 hours after dosing). Cohort 4 will include up to 15 patients (8 to 12 active and 2 to 3 placebo).*

In Cohorts 1, 2 and 3, RO7020531 or matching placebo will be administered together with patient's NUC treatment (tenofovir, entecavir, adefovir, or telbivudine either as single agents or in combination). NUC(s) will be administered per local label. On the day of study visits, patients will take study treatment together with NUC(s) in clinic.

In Cohort 4, RO7020531 or matching placebo will be administered alone.

The qualified individual responsible for dispensing the study drug will dispense to the patient the correct bottles of RO7020531 and/or matching placebo according to the IxRS assignment. This individual will write the date dispensed and patient number on the study drug bottle label and on the Drug Accountability Record. This individual will also record the study drug batch or lot number received by each patient during the study.

Guidelines for treatment discontinuation are provided in Section 4.7.

Accountability and patient compliance will be assessed by maintaining adequate study drug dispensing records. Information about patient compliance should be captured in an electronic Case Report Form (eCRF). The data should include information about any missing doses or other dosing errors throughout treatment period.

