## **Part 2: Chronic Hepatitis B Patients**

Individual patients must discontinue RO7020531/placebo if they experience any of the following:

- Safety and tolerability issues, e.g., flu-like symptoms not tolerable and not manageable with symptomatic/*prophylactic* treatment with acetaminophen (*paracetamol*) and/or dose reduction of RO7020531 (*Cohort 4 only*).
- Grade 4 ALT (i.e.,  $\geq 10 \times \text{ULN}$ ) as defined by the Division of Acquired Immunodeficiency Syndrome (AIDS) Table for Grading the Severity of Adult and Pediatric Adverse Events (“DAIDS AE grading table”) ([Appendix 6](#)), confirmed within 48-72 hours.
- Grade 3 ALT (i.e.,  $> 5 \times \text{ULN}$ ) combined with total bilirubin  $> 2 \times \text{ULN}$  (of which  $> 35\%$  is direct bilirubin), or Grade 3 ALT and  $\text{INR} > 1.5$ .
- Grade 4 hematology ( $\text{Hb} < 7.0 \text{ g/dL}$ , absolute neutrophil count  $< 400 /\text{mm}^3$ , absolute lymphocyte count  $< 350/\text{mm}^3$ , or platelets  $< 25,000/\text{mm}^3$ ).
- Any other confirmed (within 48-72h) Grade 3/4 laboratory abnormality deemed clinically significant (based on Investigator’s assessment).
- Development of liver decompensation (ascites, varices, Child-Pugh Class B or C clinical classification).
- Confirmed virological breakthrough after ascertaining that patients are compliant with treatment administration.
- For Cohorts 1, 2 and 3: NUC analogue discontinuation due to safety issues or resistance development.

If 4 or more out of 15 patients (12 receiving RO7020531 and 3 receiving placebo) are discontinued for drug-related safety reasons, enrollment will be halted and safety analysis will be performed. The results of the safety analysis will be provided to IEC/IRB and/or Health Authority, if applicable, before resuming enrollment.

Patients who discontinue study drug before the end of 6-week treatment period:

- Will not resume dosing with RO7020531/placebo. Dosing with NUC analogue in Cohorts 1, 2 and 3 will continue per each patient’s physician discretion and local label.

All prematurely discontinued patients will be asked to come back for an unscheduled visit (see Section 4.6.2.4) to have assessments performed as listed in the SoA (Appendix 1) under “Study Drug Discontinuation / Early Termination”.

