## Appendix 1 Schedule of Assessments: CHB Patients on NUCs (Part 2 Cohorts 1, 2 & 3)

- a) Visits Day 21/22 can be also conducted on Day 19/20 or Day 23/24.
- b) Visits Day 41/42 can be also conducted on Day 39/40.
- c) Visits Week 9 and Week 12 have window  $\pm 5$  days.
- d) Eligibility criteria must be confirmed by Day -1.
- e) Medical history should include detailed HBV history.
- f) Full physical exam, including recording of weight, is required at screening, Day -1, Day 42 and Week 12. Basic and/or symptoms-directed physical examination (at least lungs, cardiovascular, abdomen, extremities, lymph nodes) should be performed on Day 21 (no recording of weight required). At all other visits (or as clinically indicated), limited, symptom-directed physical examinations should be performed at the discretion of the Investigator. Height will only be recorded at screening. BMI will be calculated at screening.
- g) Vital signs include blood pressure, pulse rate, respiratory rate and body temperature. Blood pressure, respiratory rate and pulse rate will be obtained after the patient has been in a supine or sitting position for at least 5 minutes. Blood pressure measurement will be performed in triplicate (can be as short as 20 second to 1 minute interval between measurements).
- h) 12-lead ECGs will be obtained in triplicate (three consecutive interpretable 12-lead ECGs within a 2–5 minute interval) after the subject has been in a supine position for at least 10 minutes. Automated ECG intervals (PR (PQ), QRS, QT, QTcF) and HR will be captured or calculated, and the changes in T-wave and U-wave morphology will be documented.
- i) During treatment period, samples for clinical laboratory tests (hematology, chemistry, coagulation, urinalysis) should be collected in the morning pre-dose (before taking NUC treatment or/and study drug). At all other time-points, these samples should be taken at the most appropriate time.
- j) Serum or plasma beta-human chorionic gonadotropin ( $\beta$ -HCG) at screening, urine on all other occasions (females only).
- k) Study drug will be administered together with patient's nucleos(t)ide analogue treatment in fasted state.
- l) Time-points for PK and/or PD assessments 24 hours after study drug dosing on previous day.
- m) B-cell activation panel may be assessed at selected sites only.
- n) Alpha-fetoprotein not required if subject was re-screened within a 6 month period.

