Medical History f	X																		
Physical Examination g	X	X								X					X	X		X	
Vital Signs h	X	X	6	X	4 or 5 i	4 or 5 i	3	X	X	X	X	X	X	X	X	X	X	X	
ECG-12 lead j	X	X	X	X	X	X		X							X	X		X	
Hematology, Blood Chemistry, Coagulation k	X	X		X		X		X		X				X		X	X	X	
Urinalysis l	X	X		X		X		X		X				X		X	X	X	
Pregnancy Test k	X	X													X	X		X	
Administration of Study Medication l			X		X	X	X		X	X				X	X				
Randomisation			X																
RO PK Sample			7	X m	2	2	2			2				7	X m				
PD for Protein Biomarkers		X	2	X m	2	2	2	X m		2	X m			2	X m	X	X	X	
Whole Blood for RNA		X	2	X m	2	2	2	X m		2	X m			2	X m	X	X	X	
Immunophenotyping		X								X					X	X		X	

**Appendix 1 Schedule of Assessments:  
CHB Patients Who Are Not on Antiviral Treatment (Part 2 Cohort 4) – 2**

Visit	Screening	Treatment Period															Follow Up Visit	Follow Up Visit
Day	D-28 to D-2	Day -1	Day 1	Day 2	Day 3	Day 5	Day 7	Day 8	Day 15 a	Day 21 a	Day 22 a	Day 28 a	Day 35 a	Day 41 a	Day 42 a	Study Drug Discontinuation / Early Termination	Week 9 a	Week 12 a
HBV DNA, HBV TNA, viral resistance monitoring 	X	X						X	X	X		X	X		X	X		X
HBsAg, HBeAg, HBcAg, HBsAg/anti-HBsAg complex	X	X								X					X	X		X
anti-HBs, anti-HBe, anti-HBc	X	X													X	X		X
HBV Viral Genotyping		X																
Autoimmune panel, Thyroid function, Alpha-fetoprotein 	X																	
Viral Serology (HAV, HCV, HDV, HEV, HIV)	X																	
Follicle Stimulating Hormone 	X																	
Substance Use 	X	X																
Liver Biopsy/Fibroscan 	X																	
Whole Blood for RBR DNA 			X															
Clinical Genotyping 			X															
Adverse Events, Previous and Concomitant Treatments	X u	X u	X	X	X	X	X	X	X	X	X	X	X	X	X	X	X	X

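### Part 2 schedules no pregnancy test between Day -1 and the end-of-treatment visit, so the instruction to stop study drug on pregnancy has no scheduled check behind it during dosing

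*Combined protocol and SAP*

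**What the plan says.** **The action on pregnancy.** Section 5.3.9.1 (under reporting requirements for pregnancies) states: "The Investigator should discontinue study drug and counsel the HV/patient, discussing the risks of the pregnancy and the possible effects on the fetus". It also gives a route by which the investigator learns of it: a woman of childbearing potential "will be instructed to immediately inform the Investigator if she becomes pregnant until the end of the follow-up period".

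**Dosing.** Section 4.4.2.1, Part 2, has RO7020531 or placebo given "every other day from Day 1 through to Day 41", with an exception for Cohort 4 patients moved to weekly dosing. It adds: "In total, up to 21 doses will be given".

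**Testing.** Section 4.2.2.2 requires for entry: "Negative pregnancy test on Day -1 for female patients". In Appendix 1, the pregnancy-test rows of both Part 2 schedules are marked at screening, Day -1, Day 42, the study drug discontinuation/early termination visit and Week 12. Section 4.6.1.5 specifies serum or plasma at screening and urine on the other occasions, and names no on-treatment occasion.

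**Discontinuation.** The opening of Section 4.7.1.1 includes pregnancy among the grounds on which an investigator has the right to withdraw someone from the study. The Part 2 list later in that section begins "Individual patients must discontinue RO7020531/placebo if they experience any of the following", and pregnancy is not in it.

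**The concern.** An instruction to stop a drug when a condition arises works only as well as the means of learning that the condition has arisen. Here the instruction applies during dosing, but the first scheduled post-baseline test comes at the end of dosing. A pregnancy too early to show on Day -1, or conceived in the first weeks of treatment, would meet no scheduled test while most or all doses were being given. Each cohort must include at least two females, so the affected group exists by design, although not every woman need be of childbearing potential.

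The second issue is wording. A site that consults 4.7.1.1 for the stopping criteria finds a discretionary right to withdraw and a mandatory list without pregnancy. It has to look in the reporting section, 5.3.9.1, for the instruction to discontinue study drug.

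**Working it through.** **1. Dose count (the plan's own figure).** Every-other-day dosing on odd days from Day 1 to Day 41 gives (41 − 1)/2 + 1 = 21 doses, the last on Day 41. This reproduces the stated maximum of 21.

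**2. Reading the schedule rows.** The tables are imperfectly converted from PDF, so the column positions were checked against the physical-examination row. That row carries the same marks as the pregnancy-test row plus Day 21. Its footnote spells the days out: "Full physical exam, including recording of weight, is required at screening, Day -1, Day 42 and Week 12", with a basic examination on Day 21. The two agree. In the Cohorts 1 to 3 table the last mark of both rows sits one column beyond the printed headers. Both rows shift alike, so this is a conversion artefact and the mark is Week 12. Pregnancy tests marked from Day 1 to Day 41: 0 in Cohorts 1 to 3 and 0 in Cohort 4.

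**3. Length of the gap.** There is no Day 0.

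| End-of-treatment visit | Day of test | Days since Day -1 | Doses given before the test |
|---|---|---|---|
| Day 41/42 | 42 | 42 + 1 − 1 = 42 | 21 |
| Day 39/40 (window in 4.6.2.2) | 40 | 40 + 1 − 1 = 40 | (39 − 1)/2 + 1 = 20 |

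In the second row the documents do not say whether a Day 41 dose follows. If it does, the test precedes at most 1 of the 21 doses. The test at the discontinuation/early termination visit is done after the drug has been stopped, so it cannot prompt the stop.

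**4. What an existing sample could offer.** Urinalysis is already scheduled at the Day 21 visit in both schedules, and the footnotes require it before dosing. Doses remaining, counting the one on the visit day:

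- visit on Day 19: (41 − 19)/2 + 1 = 12
- visit on Day 21: (41 − 21)/2 + 1 = 11
- visit on Day 23: (41 − 23)/2 + 1 = 10

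Cohort 4 patients on weekly dosing have fewer.

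**5. How far such a test would reach.** The documents give no detection lag. Assume that urine turns positive 10 to 16 days after conception. A Day 21 test then finds conceptions up to Day 21 − 16 = 5 at the long lag and up to Day 21 − 10 = 11 at the short lag. Later conceptions would still be missed.

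**6. Who is left to benefit.** Section 1.2.2 reports 30 patients in Cohorts 1 to 3 and 9 in Cohort 4 dosed by 01 May 2020. Section 4.2 plans about 20 to 30 and up to 15. At most 15 − 9 = 6 Cohort 4 places remained at that date, only some of which would go to women.

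**7. The three wordings on pregnancy.**

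| Place | Force | Object |
|---|---|---|
| 5.3.9.1 | investigator should act | study drug |
| 4.7.1.1, opening | investigator has the right to act | study participation |
| 4.7.1.1, Part 2 list | mandatory stops; pregnancy absent | study drug |

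**The case against.** The strongest reply is that the plan does not contradict itself on testing. Section 5.3.9.1 is triggered by learning of a pregnancy, names self-report as the route, and promises no on-treatment test. Whether to schedule one is a design choice. That is right, and the point is put as a gap in support for the instruction.

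A reader might infer that the stop can operate only if the patient tests herself, or that a pregnancy would necessarily pass through the whole course unseen. The documents do not support either reading. Section 4.6.2.4 allows unscheduled safety assessments at the investigator's discretion, Section 4.6.1.5 allows extra blood or urine samples when symptoms call for them, and Section 5.3.1 has investigators ask about adverse events at each contact. What is missing is a scheduled check.

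A reader might also infer that 4.7.1.1 ignores pregnancy or flatly conflicts with 5.3.9.1. It does neither. Its opening names pregnancy, and the absence of a should-level instruction from a must-level list is a difference of force.

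The mitigations also stand. Women of childbearing potential must abstain or use two contraceptive methods, one of them a barrier (4.2.2.2). The Day -1 test must be negative. The GLP embryo-fetal studies in rats and rabbits showed no teratogenicity or embryo-fetal toxicity, other than more frequent non-adverse skeletal variations (1.2.1.4). These lower the expected number and the stakes, but they do not supply the missing check.

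**Conclusion.** The point holds as a minor one. No scheduled pregnancy test in Part 2 falls between Day -1 and the end-of-treatment visit, a gap of 40 to 42 days containing 20 or 21 every-other-day doses. During dosing the discontinuation instruction in 5.3.9.1 depends on self-report or on discretionary assessment. Separately, the opening of 4.7.1.1, its Part 2 list and 5.3.9.1 give pregnancy three different treatments and should be brought into line.

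The benefit of closing the gap is small. It falls mainly on the remaining Cohort 4 patients, and a single mid-course test would catch only early conceptions. The schedule reading rests on the column check described above. The reach of a Day 21 test rests on the assumed lag of 10 to 16 days, which the documents do not give.

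**What to change.** - Reconcile both Part 2 schedules in Appendix 1 with Section 5.3.9.1, so that a scheduled on-treatment pregnancy check supports the instruction there. The pre-dose urine at the Day 21 visit is an existing sample on which this could be done.
- Reconcile the opening of 4.7.1.1, the Part 2 list in 4.7.1.1 and Section 5.3.9.1, with cross-references, so that a site finds the same statement about pregnancy wherever it looks. Which stopping rule applies is for the sponsor to decide.

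The cost is one urine dipstick per female patient and an amendment entry. No new visit or blood draw is needed. For Cohorts 1 to 3, where 30 patients had already been dosed, the schedule change probably comes too late to matter; the wording would still be worth correcting before it is reused.

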#### **5.3.9.2 Pregnancies in Female Partners of Male Subjects**

Male HVs/patients will be instructed through the Informed Consent Form to immediately inform the Investigator if their partner becomes pregnant during the study until the end of follow up period (28 days after the last dose of study drug for Part 1 and 6 weeks after the last dose for Part 2). A Clinical Trial Pregnancy Reporting Form should be completed by the Investigator and submitted to the Sponsor within 24 hours after learning of the pregnancy. Attempts should be made to collect and report details of the course and outcome of any pregnancy in the partner of a male HV/patient exposed to study drug. The pregnant partner will need to sign an Authorization for Use and Disclosure of Pregnancy Health Information to allow for follow-up on her pregnancy. Once the authorization has been signed, the Investigator will update the Clinical Trial Pregnancy Reporting Form with additional information on the course and outcome of the pregnancy. An Investigator who is contacted by the male HV/patient or his pregnant partner may provide information on the risks of the pregnancy and the possible effects on the fetus, to support an informed decision in cooperation with the treating physician and/or obstetrician.

